Due to patient breathing, FDG PET quantitation may become susceptible to breathing-induced uncertainties, which may reduce the prognostic and predictive values of FDG-PET. Breath-Hold PET/CT acquisition has been shown to improve the accuracy of PET quantitation. In contrast to the study by Kong et al. (11), we will therefore measure the prognostic and predictive values of FDG PET using BH PET data, and compare those with results deduced from the free-breathing data sets. Due to the improved accuracy of BH-PET quantitation, we expect BH data would yield improved prognostic values over those of the FB PET.

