## **4.0 OVERVIEW OF STUDY DESIGN/INTERVENTION**

### **4.1 Design**

This is a single-institution exploratory study evaluating the prognostic and predictive significance and reproducibility of tumor hypoxia as imaged by F-FMISO PET, in NSCLC patients before receiving any treatments for their disease. In a sub-group of these patients, we will assess the predictive value of F-FDG PET/CT as well. Moreover, in a sub-group of five patients, we will assess the feasibility of simultaneous F-FMISO/F-FDG acquisitions. Patients will be identified in thoracic oncology, radiation oncology, or radiology departments at the time of their planned diagnostic imaging studies.

We will also evaluate the pharmacokinetic properties of F-FMISO during the imaging studies. Moreover, we will evaluate the significance of breath hold (BH) imaging over standard techniques in both F-FDG PET/CT and F-FMISO PET/CT image sets in patients from Group 1, as outlined in Sections 9.1 and 9.2. Patients will be identified and consented prior to their baseline F-FDG-PET/CT. A total of 25 patients will be accrued for this study over a 3 year period; 10 patients who are receiving RT or concurrent chemo RT and 16 patients who are receiving neoadjuvant chemotherapy. The group of 10 patients receiving RT or concurrent chemo-RT will receive an additional repeat F-FDG PET/CT scan at mid-treatment.

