Therefore, data from both groups of patients will be analyzed together. Historical data suggests 38% of patients will be free of recurrence at 3 years (53), which provides us with approximately 80% power to detect a hazard ratio of 3.0 between groups of low and high change. This calculation is based on a log-rank test and assumes that extent of hypoxia is dichotomized at observed median resulting in equal group sizes and maximal power. This is for planning purposes only. We will use Cox regression with extent of hypoxia as the covariate in two different ways: (1) lesion-based analysis with an estimating equations to account for multiple observations per patient; (2) patient-based where an aggregate measure of extent of hypoxia (sum of the fraction of tumor volumes with  $k3 > 0.1$  across all lesions) over all lesions within a patient) will be used as a covariate. In addition, a lesion and patient-based analyses for presence of hypoxia will also be considered where, for the patient-based analysis, the aggregate measure will be defined as presence of hypoxia in at least one of the lesions.

In an exploratory analysis to address the secondary objective of assessing the predictive value of FDG PET/CT in a group of twenty five lung cancer patients undergoing radiotherapy or concurrent chemoradiotherapy, we will use the concordance probability estimate from a proportional hazards regression model with SUV as the predictor for the outcomes of survival and progression-free survival. Time of origin will be the start time of therapy (neoadjuvant therapy, if applicable, concurrent chemoradiation or radiation alone otherwise). We will use these estimates to preliminarily determine whether BH PET/CT provides greater predictive capability than Free-Breathing (FB) PET/CT. Since these analyses are exploratory findings will be interpreted as hypothesis-generating.

We expect to accrue one patient a month for each of the two cohorts.

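### The index used to compare breath-hold with free-breathing FDG ignores the direction of the association and cannot fall below 0.5; Section 14 should fix the covariate and its expected sign.

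*Combined protocol and SAP*

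**What the plan says.** Section 14.0 (Biostatistics) addresses the secondary FDG objective as follows: "we will use the concordance probability estimate from a proportional hazards regression model with SUV as the predictor", with survival and progression-free survival as outcomes. On the comparison it says: "We will use these estimates to preliminarily determine whether BH PET/CT provides greater predictive capability than Free-Breathing (FB) PET/CT". It adds: "Since these analyses are exploratory findings will be interpreted as hypothesis-generating".

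Section 14 gives no expected sign for the SUV coefficient. It does not require the two fits to share a sign, does not ask for the hazard ratio beside the index, and gives no interval or test for the difference. It calls the covariate only SUV. The Schema in Section 1.0 is more specific: the predictor there is the change in lesion SUVpeak from baseline to the mid-treatment scan.

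A direction appears only as background. Section 3.1 cites a pilot study in which a large fall in FDG uptake went with longer survival. The same section states an expectation about the image sets, "we expect BH data would yield improved prognostic values over those of the FB PET", but that concerns which set does better, not the sign of the association.

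The number of patients is given in two ways. Section 14 speaks of "assessing the predictive value of FDG PET/CT in a group of twenty five lung cancer patients", while Section 4.1 says "The group of 10 patients receiving RT or concurrent chemo-RT will receive an additional repeat" FDG scan. Both sizes are used below.

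**The concern.** The question is which image set predicts outcome better. A useful index for that should give about 0.5 when there is no prediction and less than 0.5 when patients are ranked the wrong way round. The model-based concordance probability estimate does neither, because the fitted coefficient absorbs the direction. An image set in which a larger fall in uptake happens to go with worse survival earns the same score as one in which it goes with better survival. If both sets lean the wrong way, the more strongly wrong one ranks first.

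With so few patients, a chance reversal of sign is quite possible when the true association is weak. The study would then carry forward a BH against FB ranking, and an impression of predictive value, that the data do not support. A confidence interval for the difference between two unsigned estimates would not supply the missing direction.

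**Working it through.** The plan states no figure for this comparison, so there is none to reproduce. The check has an algebraic part, which needs no assumptions, and a simulation, which does.

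**Algebra.** Under proportional hazards with one covariate x and fitted coefficient b, patients i and j contribute 1/(1+exp(−|b(xi−xj)|)), and the index is the mean over all pairs.
- Each term is at least 0.5, so the index is too.
- Replacing b by −b changes nothing.
- Example: for a pair one unit apart, b=+0.7 and b=−0.7 both give 1/(1+exp(−0.7)) = 1/1.497 = 0.668. A directed score (higher x expected to be worse) gives 0.668 for b=+0.7 and 1−0.668 = 0.332 for b=−0.7.
- On one simulated set of 25 values, the index is 0.576 at b=±0.35, 0.641 at b=±0.7, 0.686 at b=±1.0 and 0.500 at b=0.

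**Simulation inputs from the documents.**
- Event rate (Section 14): "Historical data suggests 38% of patients will be free of recurrence at 3 years". With exponential times the hazard is −ln(0.38)/3 = 0.323 per year.
- Follow-up (Section 12.0): at most 3 years.
- Size: 25 (Section 14) or 10 (Section 4.1). Expected events are 25×0.62 = 15.5 or 10×0.62 = 6.2.

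**Inputs assumed, not in the documents.** BH and FB each correlate 0.92 with the true signal. The hazard ratio (HR) per SD of the true signal is 1.0, 1.25, 1.5 or 2.0.

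**No true association.** The mean index is about 0.56 at n=25 and exceeds 0.60 in about one trial in five. At n=10 the mean is about 0.61 and it exceeds 0.60 in about 45% of trials. A directed Harrell C averages 0.50. The lowest index in any run was 0.500.

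**How often the higher-scoring set has the wrong sign, n=25 (approximate):**

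| HR per SD | Wrong-signed set beats right-signed set | Both sets wrong-signed | Sum |
|---|---|---|---|
| 1.0 | 9% | 40% | 49% |
| 1.25 | 6% | 14% | 20% |
| 1.5 | 2.5% | 4% | 6.5% |
| 2.0 | 0.4% | 0.6% | 1.0% |

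At n=10, a wrong-signed set beats a right-signed one in about 10%, 7%, 5% and 3% of trials.

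**Sensitivity to the assumed correlations, n=25.** With BH/FB correlations of 0.95/0.90, 0.95/0.70 and 0.80/0.60, the first type of misranking occurs in 8.5% to 17.4% of trials with no association, 6% to 12% at log HR 0.2 per SD, 4% to 8% at 0.35 and 0.2% to 1.6% at 0.7.

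**One simulated trial, picked as an illustration** (25 patients, 18 events, high SUV taken as worse). BH has HR 0.887 per SD, the wrong way, and index 0.535. FB has HR 1.013, the right way, and index 0.504. The plan's comparison favours BH. With the wrong-sign fit scored as 1 minus the estimate, BH becomes 1−0.535 = 0.465 and falls below FB.

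**Effect of the sign rule.** A right-signed fit then always scores at least 0.5 and a wrong-signed one at most 0.5, so the first column of the table becomes zero. The second column stays, because it is sampling error, but both sets then show below 0.5.

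**The case against.** The strongest case on the other side has four parts.

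*The documents limit the use.* The analysis is secondary, its determination is only preliminary, and its findings are hypothesis-generating. Sections 1.0 and 3.3 say the scan results will not change management. This stands, and it limits the weight of the point. A reader might infer that the trial will formally declare a wrong-way image set the better predictor; no declaration rule or threshold exists, so the documents do not support that.

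*The sum column overstates misranking.* A reader might take 49%, 20% and 6.5% as the rate at which the index picks the wrong set. It is not. Most of those trials have both sets wrong-signed, and a directed index would also put a wrong-signed set first in about 40%, 14%, 4% and 0.6% of trials, although it would show it below 0.5. BH and FB are also equally good by construction in the main simulation, so it cannot show a truly better set losing. Where the signs split at n=25, the winning index averages only about 0.54 and the gap is 0.02 to 0.03. All this stands.

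*The sign is visible.* The index comes from a fitted Cox model, so the analyst can see the coefficient. True, but Section 14 does not ask for it to be reported or used.

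*Section 14 gives no formula, and changing the index is partly preference.* A rank-based c-index on the fitted linear predictor would dip below 0.5 in 11% to 12% of runs with no association, so the floor would not be strict; the fitted sign would still absorb the direction. Harrell or Uno C is slightly more variable and depends on censoring, which matters with about 15 events. The documents therefore give no ground for saying that the concordance probability estimate must be abandoned.

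**Conclusion.** The point holds in limited form. The floor at 0.5 and the indifference to sign follow from the definition of the index, and Section 14 has no safeguard against either. The mean of about 0.56 (n=25) or 0.61 (n=10) with no association rests on the documents' event rate and follow-up, plus exponential survival and a normally distributed covariate. The misranking rates in the table rest further on the assumed correlation of 0.92 and the assumed hazard ratios; other correlations roughly halve or double them.

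The problem matters when the true association is weak or absent and nearly vanishes at HR 2.0 per SD. The documents give no FDG effect size, and Section 3.1 treats the value of FDG as an early response marker during radiotherapy as unsettled, so the weak case cannot be set aside. Nor can any sign be called right or wrong until Section 14 says which SUV measure is the covariate. The change is worth making, but it does not threaten the study's main results.

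**What to change.** In Section 14:
- Name the covariate as the change in SUVpeak from baseline to mid-treatment, in line with the Schema, and state the expected direction: a smaller fall means a higher hazard.
- Report the signed hazard ratio beside each concordance probability estimate, for BH and for FB.
- Score a fit with the unexpected sign as 1 minus its estimate, and call neither image set the better predictor unless its association has the expected sign.

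A directed Harrell or Uno C can be added as an optional sensitivity analysis. It is slightly more variable and depends on the censoring pattern, which Uno weights address.

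The cost is one sentence in Section 14 and a small change in code. No extra patients, scans or data are needed. The rule does not remove sampling error: with 10 or 25 patients, both sets may still come out wrong-signed, but the report will then show it.

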## 2.0 OBJECTIVES AND SCIENTIFIC AIMS

The primary objectives of this study are:

- To correlate the presence and extent of hypoxia, as defined by F-FMISO FB and BH PET/CT at baseline with 3-year progression-free survival (PFS) and overall survival (OS).
- To assess the predictive value of F-FMISO PET/CT in lung cancer patients undergoing radiotherapy or concurrent chemoradiotherapy, as measured by Breath-Hold (BH) and Free-Breathing (FB) PET/CT images, and to determine whether BH PET/CT provides greater predictive capability than Free-Breathing (FB) PET/CT.

The secondary objective of this study is:

- To assess the predictive value of F-FDG PET/CT in a group of twenty five lung cancer patients undergoing radiotherapy or concurrent chemoradiotherapy, as measured by Breath-Hold (BH) and Free-Breathing (FB) PET/CT images, and to determine whether BH PET/CT provides greater predictive capability than Free-Breathing (FB) PET/CT.

- To assess the feasibility of simultaneous F-FDG and F-FMISO PET dynamic acquisitions in a group of 5 patients undergoing radiotherapy or concurrent chemoradiotherapy. If successful, our approach would allow multi-radiotracer PET exams on the same day reducing the need for extra patient visits. For the patients who will undergo the dual FMISO/FDG study, the mid-treatment FMISO will be optional.

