To ensure patient safety, vital signs and toxicity assessments will be performed immediately after each scan session. Additionally, approximately 24 hours (or on the next business day) after the completion of each scan session, a toxicity assessment will be completed via a telephone followup.

Only patients in Group 1 will participate in BH scans.

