## **12.0 CRITERIA FOR THERAPEUTIC RESPONSE/OUTCOME ASSESSMENT**

There are two primary goals for this study; first, to assess the reproducibility of kinetic analysis of dynamic  $^{18}\text{F}$ -FMISO PET images, in both BH and FB data sets, and second, to assess the prognostic value of hypoxia, as measured with  $^{18}\text{F}$ -FMISO PET, with OS and PFS in NSCLC. As explained above, the presence and extent of tumor hypoxia will be measured by means of kinetic analysis of dynamic  $^{18}\text{F}$ -FMISO PET images. Kinetic analysis parameters may be susceptible to breathing-induced motion artifacts due to patient respiration. Hence, the correlation of outcome to both the presence and extent of tumor hypoxia may be inaccurate. We will therefore conduct analyses based on BH- and FB- PET datasets, and then compare the results in order to assess the effect breathing on these parameters. This exploratory objective of tumor hypoxia correlation to clinical endpoints is dependent on time to tumor progression and death. We will follow up with these patients up to a maximum of three years. The table below summarizes the milestones of this research project.

Likewise, the predictive value of FDG PET may also be suspect due to breathing motion artifacts. In light of the discussion above, therefore, the secondary aim is to compare the predictive value of FDG PET when the data are acquired in BH versus in FB PET.

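### Breath-hold versus free-breathing PET is to be compared through in-sample concordance estimates with no interval for the paired difference (FDG), and with no named contrast at all for the primary FMISO objective

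*Combined protocol and SAP*

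**What the plan says.** **FDG (secondary objective).** Section 14.0 states that "we will use the concordance probability estimate from a proportional hazards regression model with SUV as the predictor", for survival and for progression-free survival. It continues: "We will use these estimates to preliminarily determine whether BH PET/CT provides greater predictive capability than Free-Breathing (FB) PET/CT". It then qualifies the analysis: "Since these analyses are exploratory findings will be interpreted as hypothesis-generating". No standard error, interval, paired test, margin or threshold is given for the BH–FB difference.

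**FMISO (primary objective).** The second primary objective in Section 2.0 is to assess the predictive value of FMISO, "as measured by Breath-Hold (BH) and Free-Breathing (FB) PET/CT images, and to determine whether BH PET/CT provides greater predictive capability than Free-Breathing (FB) PET/CT". The outcome analysis in Section 14.0 is "We will use Cox regression with extent of hypoxia as the covariate in two different ways", with a parallel analysis for presence of hypoxia. It does not say whether BH or FB data supply the covariate, and it sets out no contrast between them. Section 12.0 adds the intention: "We will therefore conduct analyses based on BH- and FB- PET datasets, and then compare the results". It names no metric.

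**Numbers.** Section 14.0 places 25 radiotherapy or chemoradiotherapy patients in the FDG analysis. Section 4.1 gives 10 such patients.

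**The concern.** Two concordance estimates from the same small group will almost never be equal, so one method will come out ahead even when they predict equally well. Without an interval for the difference, a reader cannot tell a real advantage from noise. Section 3.1 already states an expectation that BH will do better, so a chance result in that direction would look like confirmation. For FMISO the gap is wider: a question listed as primary has no stated measure, so the comparison could be made in several ways after the data are seen.

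**Working it through.** **The plan's own figure.** None is given for BH versus FB. The only design figure is about 80% power for a hazard ratio of 3.0 between low and high hypoxia, a different question. For the record, events = 25 × (1 − 0.38) = 15.5. Schoenfeld's formula gives z = (√15.5 / 2) × ln 3 − 1.96 = 2.16 − 1.96 = 0.20, or 58% power at two-sided 5%. At one-sided 10% it gives 2.16 − 1.28 = 0.88, or 81%. The plan states no significance level, so the figure can be neither confirmed nor rejected, and the point below does not depend on it.

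**Inputs from the documents**
- 25 patients (Sections 13.0 and 14.0), or 10 on radiotherapy (Section 4.1).
- 38% recurrence-free at 3 years (Section 14.0), so 15.5 events in 25 patients or 10 × 0.62 = 6.2 in 10.
- Follow-up to 3 years (Section 12.0).

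**Assumed, because the documents are silent**
- Hazard ratio per SD of the underlying marker: 1.0 to 3.0.
- Reliability of the BH reading 0.80–0.95 and of the FB reading 0.50–0.80.

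**Method.** Each simulated patient has one underlying marker value, read once by BH and once by FB with independent error. Survival is exponential, with 38% censored at 3 years. A univariable Cox model is fitted to each reading. The concordance probability estimate is the mean over patient pairs of 1 / (1 + exp(−|b(xᵢ − xⱼ)|)), where b is the fitted coefficient. There were 4,000 runs per setting.

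**Results when the methods are equal or the marker is useless.** At n = 25, BH has the larger estimate in 48–51% of runs. A useless marker has a mean concordance of 0.56 at n = 25 and 0.61 at n = 10, because the formula cannot return less than 0.5. This optimism falls on both methods alike: with a useless marker the mean BH–FB difference is about 0.

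**Results when BH is truly better**

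| HR per SD; reliability BH v FB | n | Mean gain | SD of difference | BH ranked higher |
|---|---|---|---|---|
| 2.0; 0.9 v 0.7 | 25 | 0.020 | 0.048 | 66% |
| 3.0; 0.9 v 0.8 | 25 | 0.014 | 0.044 | 63% |
| 3.0; 0.9 v 0.7 | 25 | 0.032 | 0.049 | 74% |
| 3.0; 0.95 v 0.6 | 25 | 0.055 | 0.052 | 86% |
| 3.0; 0.9 v 0.5 | 25 | 0.064 | 0.062 | 86% |
| 2.0; 0.9 v 0.7 | 10 | 0.014 | 0.083 | 57% |
| 3.0; 0.95 v 0.6 | 10 | 0.049 | 0.090 | 72% |

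At n = 25 the share is 56–65% for a hazard ratio of 1.5 per SD, 59–76% for 2.0 and 63–86% for 3.0. At n = 10 the shares are 53–55%, 56–62% and 57–72%. Widening the reliability gap to 0.95 v 0.5 at a hazard ratio of 3.0 raises the upper ends to about 89% and 74%, with a gain of about 0.07.

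**Cross-check.** The share should be close to Φ(gain / SD). For the first row, Φ(0.020 / 0.048) = Φ(0.42) = 66%. For the fourth, Φ(0.055 / 0.052) = Φ(1.06) = 86%.

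**What an interval would look like.** Half-width ≈ 1.96 × SD. At n = 25 this is 1.96 × 0.038 = 0.07 to 1.96 × 0.062 = 0.12. At n = 10 it is 1.96 × 0.068 = 0.13 to 1.96 × 0.102 = 0.20. The chance that the interval excludes 0 in BH's favour is about Φ(gain / SD − 1.96): Φ(0.42 − 1.96) = 6% for the moderate gain and Φ(1.06 − 1.96) = 18% for a large one. A percentile bootstrap run directly on 150 simulated trials gave about 5% and 19% at n = 25, and about 1% for the moderate gain at n = 10.

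**The case against.** The strongest reply is that the plan claims little. The FDG text speaks of a preliminary determination and of hypothesis generation, Section 4.1 calls the whole study exploratory, and Section 12.0 calls the hypoxia–outcome correlation exploratory too. Nowhere does the plan say that the larger estimate wins, and silence about an interval is not a decision to withhold one. An interval would also nearly always include 0. All of this is fair, and it makes the point one of specification. It does not remove it: an exploratory contrast still needs a measure of precision, and a primary objective still needs a named one.

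Four stronger readings are tempting and are not supported.

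- **A reader might infer that the result is close to a coin toss.** That holds if BH has little or no advantage, and nearly so in several settings with 10 patients. With 25 patients, a strong marker and a large reliability gain, the better method is ranked first in about 89% of runs. The 50% figure under equality is true of any symmetric comparison at any sample size.
- **A reader might infer from "Only patients in Group 1 will participate in BH scans" that BH and FB would be compared in different patients.** Section 4.1 confines the BH evaluation to Group 1 for both tracers. For FMISO, Sections 3.3 and 9.2 derive both image sets from one acquisition. For FDG, Section 11.1.1 acquires the extra field of view in FB and then in BH. The comparison is paired by design.
- **A reader might infer that in-sample optimism biases the comparison.** It inflates each concordance, but it cancels in the difference.
- **A reader might infer that FMISO has no outcome analysis.** Cox regression is specified, and Section 12.0 states the intention to compare. What is missing is the metric and the method of comparison.

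**Conclusion.** The point holds as a gap in specification. The FDG comparison has no planned uncertainty for the paired difference, and the primary FMISO comparison has no named contrast. At 25 patients the noise in the difference (SD about 0.04–0.06) is comparable to or larger than most of the gains considered (about 0.01–0.07). Ranking by point estimate would favour a truly better BH in about 56–89% of trials, or about 53–74% if only 10 radiotherapy patients contribute.

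The ranges rest on assumed marker strength and reliability, and on the 38% figure serving as the event-free proportion. No single value inside them can be asserted from the documents.

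**What to change.** Add one paragraph to Section 14.0, covering both tracers:

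- Restrict the comparison to Group 1 patients with both image sets.
- Report the BH minus FB difference in concordance with a 95% interval from a bootstrap that resamples patients and refits both models in each resample.
- Describe the comparison as inconclusive when the interval includes 0.
- For FMISO, name the covariate that enters the contrast. For FDG, say whether the predictor is SUV, as in Section 14.0, or the change in SUVpeak described in Section 1.0.
- Correct for optimism only if absolute concordance values are reported.
- Reconcile the 25 radiotherapy patients of Section 14.0 with the 10 of Section 4.1.

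The cost is one paragraph and a short piece of analysis code, with no new scans or data. Optimism correction, if wanted, would need nested resampling and somewhat more work. The downside is small: with a half-width of about 0.07–0.12 at n = 25 the likely report is that the comparison is inconclusive, which is a fair account of what the trial can show.
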